## 5.7. Subject Disposition

The protocol for this study makes the distinction between subject withdrawal and subject discontinuation of study treatment. Subject withdrawal occurs when a subject will no longer participate in the study (no longer taking study treatment and no longer being assessed). Subject discontinuation of study treatment occurs when a subject agrees to continue being assessed but will no longer take study treatment.

Reasons for discontinuation for all patients will be tabulated for treatment groups, and comparisons between treatment groups will be assessed by Fisher's exact test. Additionally, the median time to all-cause discontinuation will be compared between the treatment groups. The null hypothesis is that the median time to discontinuation estimated using the Kaplan-Meier product limit method will be identical for the LY3202626 dose groups and placebo. The log rank test will be used to test the null hypothesis against the alternate hypothesis that the median time to discontinuation is not the same between the groups.

## 5.8. Subject Characteristics

Standard baseline characteristics of gender, age, and race will be summarized for all patients. Treatment group comparisons will be made using Fisher's exact test for categorical data and an ANOVA with an independent factor for treatment for continuous data. Diagnosis, illness characteristics, and baseline efficacy and safety measures will be analyzed in a similar manner.

Baseline characteristics will be summarized for the efficacy and per-protocol populations by treatment group and overall. Summaries will include descriptive statistics for continuous and categorical measures. Fisher's exact test or Pearson's chi-square test will be used for treatment-group comparisons of categorical data. For continuous data, analysis of variance (ANOVA),

with independent factors for treatment, will be used. Subject characteristics to be presented include:

- Baseline AV-45 SUVr
- Baseline Tau PET SUVr
- age
- age group: 55-64, 65-74, ≥75
- gender
- race
- ethnicity
- height
- body weight
- body mass index (weight (kg) / [height (m)])
- region
- tobacco use
- alcohol use
- years of education
- work status
- ApoE4 carrier status (carrier [ε2/ε4, ε3/ε4, ε4/ε4], noncarrier [ε3/ε3, ε2/ε2, ε3/ε2])
- ApoE4 genotype (ε2/ε4, ε3/ε4, ε4/ε4, no ε4)
- having 1 or more first degree relatives with AD
- AChEI and/or memantine use at baseline
- Baseline severity of impairment as measured by ADAS-Cog13, ADCS-iADL instrumental (ADCS-iADL) and , MMSE, MoCA, NPI, ECog, BASQID , and FAQ.

Baseline characteristics will also be listed.

## 5.9. Treatment Compliance

Only subjects who consume at least 80% of the prescribed daily dose during this study will be considered compliant. The percentage of compliant subjects will be compared across treatment groups using Fisher's exact test.

## 5.10. Concomitant Therapy

Prior medications are defined as those that stop before randomization (Visit 3). Concomitant medications are defined as those being taken on or after randomization (Visit 3). A summary of

concomitant medications will be presented as frequencies and percentages for each treatment group. Fisher's exact test will be used to test for treatment differences between groups.

Medications will be coded using the World Health Organization (WHO) drug dictionary.

## **5.11. Efficacy Analyses**

### **5.11.1. Primary Outcome and Methodology**

The primary objective of this study is to assess the PD effect of 2 different LY3202626 doses (3 mg and 12 mg) in patients with mild AD dementia compared with placebo, measured by change from baseline in 18F-AV-1451 PET SUVrs at Week 52.

The primary statistical analysis is the ANCOVA, which will be used to statistically evaluate change in composite SUVr from baseline at 52 weeks post-dose. The ANCOVA will include the fixed, categorical effects of treatment dose, and the continuous, fixed covariate of baseline Tau PET SUVr and age at baseline.

Change from baseline analyses will be conducted on SUVrs computed from the following 3 composite regions with the bimodal white matter serving as the reference region: MUBADA (primary), Delta\_Z, and the frontal lobe region defined as a weighted average (weights being the number of voxels in the region) of SUV counts, averaged bilaterally, in the following Region of Interests (ROIs):

- cingulum anterior
- Inferior frontal gyrus, opercular part
- Inferior frontal gyrus, orbital part
- Inferior frontal gyrus, triangular part
- Middle frontal gyrus
- Middle frontal gyrus, orbital part
- Superior frontal gyrus
- Superior frontal gyrus, medial
- Superior frontal gyrus, orbital part

### **5.11.2. Key Secondary and Exploratory Outcomes**

The additional clinical and outcome measurements listed below will be analyzed separately using a mixed-effect model for repeated measures (MMRM) analysis.

The change from baseline score at each scheduled post-baseline visit (according to the Study Schedule - data collected at unscheduled visits, including early discontinuation visits if not matching the study schedule, will not be included in this analysis) during the treatment period will be the dependent variable. The model will include the fixed effects of treatment, visit

(categorical covariate), treatment-by-visit interaction, baseline age, baseline score (continuous covariate) and baseline-by-visit interaction. Visit will be considered a categorical variable with values equal to the visit numbers at which the scales were assessed. An unstructured covariance matrix will be used to model the within-subject variance-covariance errors. If the unstructured covariance structure matrix results in a lack of convergence, the following tests will be used in sequence: heterogeneous Toeplitz covariance structure, heterogeneous autoregressive covariance structure, heterogeneous compound symmetry covariance structure, and compound symmetry covariance structure. The Kenward-Roger approximation will be used to estimate the denominator degrees of freedom. Significance tests will be based on LSMeans using a 1-sided Alpha of 0.10. Analyses will be implemented using SAS PROC MIXED. Longitudinal graphs of the LSMeans estimates at each visit from the model will be plotted and the LSMeans and 95% confidence intervals (CIs) results will be summarized in a summary table.

The secondary outcomes that will be analyzed are the following:

- Change from baseline in ADAS-Cog13.
- Change from baseline in ADCS-iADL.
- Change from baseline in iADRS.

The exploratory outcomes that will be analyzed are the following:

- Change from baseline in MoCA total scores.
- Change from baseline in FAQ.
- Change from baseline in MMSE total scores.
- Change from baseline in ECog.

The following exploratory outcomes will be analyzed using the ANCOVA model described in Section 5.1:

- Change from baseline in NPI total scores.
- Change from baseline in BASQID total scores.

### **5.11.3. Subgroup Analyses**

To assess the effects of various demographic and baseline characteristics, subgroup analyses will be performed for the primary endpoint based on the following variables:

- Tau PET subgroup (MUBADA SUVr at baseline <1.1, 1.1-1.46, and >1.46)
- Age: 55-64, 65-74, ≥75
- ApoE4 carrier status (carrier [ $\epsilon_2/\epsilon_4$ ,  $\epsilon_3/\epsilon_4$ ,  $\epsilon_4/\epsilon_4$ ], noncarrier [ $\epsilon_3/\epsilon_3$ ,  $\epsilon_2/\epsilon_2$ ,  $\epsilon_3/\epsilon_2$ ])

The primary outcome measure will be modeled using an ANCOVA approach. This general model will include terms for baseline, treatment, subgroup, subgroup-by-treatment interaction.

## 5.12. Bioanalytical and Pharmacokinetic/Pharmacodynamic Methods

### 5.12.1. Analysis of Plasma A $\beta$

To evaluate the change in plasma A $\beta$  analytes (including assayed plasma A $\beta_{1-40}$ , A $\beta_{1-42}$ , A $\beta_{1-x}$  after treatment, an MMRM will be used to compare percent change from baseline to week 52. Log transformation will be applied to data prior to analysis and result will be back-transformed to get percent change from baseline.

The model for the fixed effects will include terms for the following independent effects: log-transformed baseline plasma A $\beta$ , treatment, visit, treatment-by-visit interaction. The dependent variable is the change from baseline in log transformed plasma A $\beta$  analytes. Visit will be considered a categorical variable with values equal to the visit numbers at which plasma A $\beta$  is assessed. A similar MMRM analysis will be performed on untransformed percent change from baseline in plasma A $\beta$  analytes if the residual analysis suggests the log transformed analysis is inappropriate.

### 5.12.2. Analysis of CSF Data

Due to very limited number patients participated in the addendum for CSF sample collection, CSF biomarkers (including CSF A $\beta_{1-40}$ , CSF A $\beta_{1-42}$ , CSF A $\beta_{1-x}$ , CSF sAPP alpha, CSF sAPP beta, CSF total tau, and CSF p-tau from lumbar puncture) will be listed by treatment by visit.

### 5.12.3. Analyses of AV-45 PET Data

The analyses of change from baseline to the post-baseline visit of the composite summary SUVR of AV-45 (amyloid imaging) normalized will be conducted using an ANCOVA model with baseline AV-45 result and baseline age as covariates and treatment as categorical effect.

Change from baseline analysis will also be conducted for SUVR of the following regions (average of right and left) normalized (based on AVID guidelines): cingulum anterior, cingulum posterior, frontal cortex, mesial temporal cortex, occipital cortex, orbitofrontal cortex, parietal cortex, and temporal cortex.

The complete listing of AV-45 parameters obtained is provided in [Appendix 4](#).

### 5.12.4. Analyses of perfusion PET Data

An additional perfusion-weighted image will be acquired at each florbetapir PET scanning visit, with no additional tracer injection, by utilizing the initial wash-in of florbetapir to the brain. These images will provide a perfusion (or blood flow) map of the brain at each time point. In AD, cerebral perfusion is reduced, especially in temporal and parietal areas, and this pattern of hypoperfusion closely mirrors the hypometabolism pattern observed using 18F-fluorodeoxyglucose (FDG)-PET. As such, the perfusion PET images provide a biomarker of resting brain function. Changes in florbetapir perfusion PET between the baseline and follow-up scans will be compared across treatment groups and to total exposure to LY3202626.

The analysis of change from baseline to the post-baseline visit of the composite summary SUVr of perfusion scan will be performed using an ANCOVA model with baseline biomarker result and baseline age as covariates and treatment as categorical effect.

The analyses of change from baseline will also be conducted for SUVr of each individual Region of Interest (ROI).

### **5.12.5. Analyses of Volumetric MRI Data**

Brain atrophy is one of the signature biological changes associated with AD, with shrinkage of the medial temporal lobe (including the hippocampus) and ventricular enlargement particularly prominent. The volume of different brain structures and measures of atrophy can be accurately quantified from vMRI scans. Magnetic resonance imaging changes in brain volume from baseline to after 52 weeks of treatment (or early discontinuation) will be quantified. Measurements of brain structural changes, including, but not limited to, whole brain, ventricles and hippocampus will be evaluated. Brain structural changes will be compared across treatment groups and to total exposure to LY3202626.

Analyses of the following vMRI parameters will be conducted:

- Right hippocampal volume ( $\text{mm}^3$ )
- Left hippocampal volume ( $\text{mm}^3$ )
- Right hippocampal volume ( $\text{mm}^3$ ) + Left hippocampal volume ( $\text{mm}^3$ )
- Right entorhinal cortex ( $\text{mm}^3$ )
- Left entorhinal cortex ( $\text{mm}^3$ )
- Atrophy of Total whole brain volume ( $\text{cm}^3$ )
- Enlargement of Ventricular volume ( $\text{cm}^3$ )

To evaluate the changes in vMRI data after treatment, an ANCOVA model will be used to compare change from baseline to 52 weeks. The change from baseline to the endpoint visit will be the dependent variable. The model for the fixed effects will include terms for the following independent effects: baseline vMRI value, age at baseline, and treatment.

In addition, annualized change in imaging biomarkers (vMRI, AV-45 and AV-1451) for each patient will be calculated using the change at the last post-baseline visit. The annualized change will be compared among the treatment groups with the same ANCOVA model described above.

## **5.13. Safety Analyses**

### **5.13.1. Extent of Exposure**

Summary statistics will be provided for the total number of subjects who were compliant by treatment group during the whole study period. The proportion of subjects who were compliant will be compared using Fisher's exact test. Only subjects who consume at least 80% of the prescribed daily dose during this study will be considered compliant.

Summary statistics will be provided for the total number of days of exposure by treatment.

### **5.13.2. Adverse Events**

Treatment-emergent adverse events (TEAEs) will be defined as events that first occurred or worsened after the randomization date (visit 3 date). Should there be insufficient data for AE start date, stop date, and time to make this comparison, the AE will be considered treatment-emergent.

Treatment-emergent adverse events will be coded according to established Medical Dictionary for Regulatory Activities (MedDRA) terms and summarized by MedDRA System Organ Class and Preferred Term.

Summaries of AEs by decreasing frequency of preferred term within system organ class will be provided for the following:

- Preexisting conditions
- TEAEs
- TEAEs by maximum severity
- TEAEs occurring in greater than or equal to 5% of subjects by preferred term
- Serious adverse events (SAEs)
- AEs reported as reason for study treatment discontinuation

These summaries will include number and percentages of subjects with TEAEs. Treatment comparisons will be carried out using Fisher's exact Test. A summary of TEAEs by visit will also be provided.

Preexisting conditions, TEAEs, SAEs, and discontinuations due to AEs will be listed.

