Patients will initially be randomized into 1 of 3 treatment groups: 2 fixed dose levels of LY3202626 (3 mg and 12 mg per day) and placebo (1:1:1) until approximately 45 participants are enrolled in each arm; then randomization will change to 1:1 with subjects entering either the 12 mg or placebo arm. Treatment duration for all subjects will be 52 weeks.

Number of Patients:

Approximately 380 patients will be enrolled for approximately 320 completed evaluable patients, assuming approximately 15% drop out.

Statistical Analysis:

Patient Characteristics:

Standard baseline characteristics of gender, age, and race will be summarized for all patients. Treatment group comparisons will be made using Fisher's exact test for categorical data and an analysis of variance (ANOVA), with an independent factor for treatment for continuous data. Diagnosis, illness characteristics, and baseline efficacy and safety measures will be analyzed in a similar manner.

Efficacy:

The primary objective of this study is to assess the effect on neuropathological progression of 2 different LY3202626 doses in patients with mild AD dementia compared with placebo, measured by change in ¹⁸F-AV-1451 PET standardized uptake value ratio (SUVr) at baseline and week 52. The primary measurement is change from

baseline ¹⁸F-AV-1451 PET SUVr at Week 52. An analysis of covariance (ANCOVA) will be used to statistically evaluate change in ¹⁸F-AV-1451 PET from baseline at 52 weeks post-dose.

Statistical analyses of mean change in efficacy and health outcome measures will be conducted. Generally, statistical assessment of the efficacy and health outcome measures will be a mixed model repeated measure (MMRM) or an ANCOVA. The primary comparison will be between LY3202626 12 mg versus placebo at endpoint.

Safety:

Safety will be assessed by summarizing and analyzing adverse events (AEs), laboratory analytes, vital signs, electrocardiograms (ECGs), skin examinations, and eye examinations during the treatment period. For continuous safety measurements, a change from baseline will be analyzed using MMRM or ANCOVA model. Safety analyses for the treatment period will include comparisons between LY3202626 dose groups and placebo. All hypotheses will be tested at a 2-sided 0.05 significance level. No adjustments for multiple comparisons will be made.

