5.1. Overall Design

Study LLCF is a multicenter, randomized, double-blind, placebo-controlled study in patients with mild AD dementia. This study (Study LLCF) will enroll patients with mild AD dementia using National Institute on Aging-Alzheimer's Association (NIA-AA) work group consensus guidelines (McKhann et al. 2011) with amyloid deposition confirmed by florbetapir F 18 PET imaging. The treatment phase will be 52 weeks.

Figure LLCF.1 illustrates the study design.

Abbreviations: AD = Alzheimer's disease; FP = follow-up period; LY = LY3202626.

Note: This is a multicenter, randomized, parallel-group, 52-week-long double-blind, placebo-controlled, study of 2 fixed dose levels of LY3202626 (3 mg and 12 mg) in patients with mild AD dementia and evidence of amyloid pathology.

Approximately 380 mild AD dementia patients will be enrolled (approximately 167 in the placebo and 12 mg groups, and approximately 45 in the 3 mg group).

Figure LLCF.1. Illustration of study design for Clinical Protocol I7X-MC-LLCF.

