10.3.7. Interim Analyses

Only the AC and Internal Review Committee (IRC) are authorized to evaluate unblinded interim safety and efficacy analyses, respectively. Study sites will receive information about interim results ONLY if results are clinically relevant for the safety of their patients. Membership of the AC and IRC will be documented in the AC charter and IRC plan. Unblinding details are specified in the unblinding plan section of the SAP or a separate document.

Details of the timing and decision criteria of the interim analyses by the AC and IRC are documented in a separate interim analysis plan and/or AC charter in order to maintain study blind, for the primary study team. If an LY3202626 dose is recommended to be dropped at the interim analysis because of safety, then randomization will be modified accordingly; in this instance, the percentage of patients receiving placebo will not be reduced.

An initial safety interim analysis will be conducted by the AC when data from approximately 130 qualified patients at 12 weeks and 40 patients through 24 weeks have been obtained. The AC may be asked to conduct additional safety interim analyses if safety concerns are observed during blinded safety monitoring. In the event that blinded safety monitoring uncovers an issue that needs to be addressed by unblinding at the group level, only members of the AC can conduct additional analyses of the safety data.

Efficacy reviews of data by an IRC may occur during the course of the study and will be documented in the IRC plan. At the times specified in Section 10.3.5, a limited number of pre-identified individuals may gain access to the unblinded PK/PD data, as specified in the unblinding plan, prior to the interim or final database lock. Information that may unblind the study during the analyses will not be reported to study sites or blinded study team until the study has been unblinded.

11. References

- American Psychiatric Association. (2013). Diagnostic and statistical manual of mental disorders (5th ed.). Arlington, VA: American Psychiatric Publishing.

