### 3. Revision History

Statistical Analysis Plan (SAP) Version 1 was approved prior to unblinding.

Statistical Analysis Plan (SAP) Version 2 was approved prior to final database lock. Due to early termination of the study, certain analyses were removed or simplified, while others were clarified. The changes in SAP version 2 are summarized below:

- Clarified that change from baseline to last observation is to be used in ANCOVA analysis if Week 52 observation is not available (Section [5.1](#))
- Removed the exploratory analysis on subjects with study partner change during the study (previously Section 5.11 in Version 1)
- Clarified the analysis for changes from baseline in NPI total score and BASQID total score will be ANCOVA instead of MMRM because they were collected only once during post-baseline visits (Section [5.11.2](#))
- Specified the cut-off for defining Tau subgroups and removed the subgroup analysis regarding race and country (Section [5.11.3](#))
- Removed sensitivity analysis on Tau PET using percentage changes from baseline (previously Section 5.12.4 in Version 1)
- Simplified analysis of CSF biomarkers to listing of values by visit by treatment due to very limited number of subjects participated in the CSF addendum (Section [5.12.2](#))
- Added analysis on annualized change in imaging biomarkers (vMRI, AV-45 PET, AV-1451 PET) because majority of the subjects would not have Week 52 observation due to early termination of the study (Section [5.12.5](#))
- Added an incidence summary for treatment-emergent CSSRS findings (Section [5.13.8.1](#))
- Simplified and clarified the analysis for categorical eye exam and eye imaging data (Section [5.13.8.3](#))

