### **5.13.3. Deaths, Other Serious Adverse Events, and Other Notable Adverse Events**

An overview of AEs, including the number and percentage of subjects who died, suffered SAEs, discontinued due to AEs and who suffered TEAEs, will be provided. Comparison between treatments will be performed using Fisher's exact Test.

In addition, the proportion of subjects within specific clusters of TEAEs will be summarized and treatment comparisons will be conducted using Fisher's exact Test. Clusters will be created from MEDRA's High Level Group Terms (HLGT) ([Table LLCF.SAP.3](#)). Each of the 3 groups with multiple HLGTS will be combined to form one cluster. Additionally, the 2 HLGTS in the skin disorder group will be analyzed separately.

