#### **5.13.4. Clinical Laboratory Evaluation**

Laboratory measurements will be analyzed using continuous data (change from baseline) and categorical or ordinal data (proportion of treatment-emergent abnormalities).

If there are multiple records of laboratory measurements at baseline or postbaseline visit, the last record will be used.

Summaries and analyses of continuous data (change from baseline) will be performed using both conventional and International System of Units (SI units).

Change from baseline to each post-baseline visit at which laboratory measurements are taken and change from baseline to the last observation will be summarized and compared between treatment groups using an ANCOVA model. For each lab analyte, the rank-transformation will be applied to the change from baseline for all subjects and all visits prior to analysis. Similarly, an independent rank-transformation will be applied to the baseline values prior to analysis. The model for the fixed effects will include terms for baseline value, treatment and age. This analysis will be done separately for each laboratory analyte.

Treatment differences in the proportion of subjects with treatment-emergent high or treatment-emergent low or treatment-emergent abnormal laboratory values at (1) anytime and (2) each post-baseline visit will be assessed using Fisher's exact test. Treatment-emergent high or low laboratory abnormality will be based on SI unit. For each laboratory analyte, only subjects who were low or normal at baseline and have at least one post-baseline measurement will be included in the denominator when computing the proportion of subject with treatment-emergent high values. Similarly, only subjects who were high or normal at baseline and have at least one post-

baseline measurement will be included in the denominator when computing the proportion of subject with treatment-emergent low values. In addition, treatment differences in the proportion of subjects who were normal at baseline and change to abnormal high or abnormal low values at any post-baseline visit will be summarized.

For urinalysis parameters, baseline to post-baseline shifts will be summarized at each visit. Likelihood ratio chi-square tests will be used to compare increase, no change and decrease shifts in urinalysis parameters between treatment groups at each visit.

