For all laboratory analytes, frequencies of subjects with notable changes (that is, increases or decreases of a prespecified amount unique to each analyte) from baseline to each postbaseline visit were also summarized for all subjects and stratified by low, normal, or high at baseline.

The proportion of subjects with treatment-emergent clinically significant changes from a low value or normal value at all baseline at any time in alanine aminotransferase (ALT), alkaline phosphatase (ALP), and total bilirubin will be summarized by treatment group. Abnormal criteria for treatment-emergent clinically significant changes are presented in [Appendix 2](#). Significant changes of interest for hepatic laboratory values are: ALT  $\geq 3$  x upper limit of normal (ULN), total bilirubin  $\geq 2$  x ULN, alkaline phosphatase (ALP)  $> 2$  x ULN, ALT  $\geq 5$  x ULN, ALT  $\geq 10$  x ULN, and total bilirubin  $\geq 2$  x ULN. Additionally, Hy's Law analysis will be conducted by comparing treatment groups with regard to the proportion of patients with (ALT  $\geq 3$  x ULN OR aspartate aminotransferase (AST)  $\geq 3$  x ULN) AND total bilirubin  $\geq 2$  x ULN. Comparisons between treatment groups will be carried out using Fisher's exact test.

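### Crude adverse-event percentages on 3 mg probably rest on longer follow-up than those on placebo, because 3 mg entered first and the study stopped early; add a time-to-first-event comparison

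*SAP*

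**What the plan says.** Allocation starts at 1:1:1 until about 45 patients are in each arm; "then randomization will change to 1:1 with subjects entering either the 12 mg or placebo arm" (Protocol Section 1, Treatment Arms and Duration). Planned sizes are "approximately 167 in the placebo and 12 mg groups, and approximately 45 in the 3 mg group" (Protocol 5.1). SAP Section 3 explains that annualized imaging change was added "because majority of the subjects would not have Week 52 observation due to early termination of the study".

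The safety set is every treated patient (SAP 5.6), so placebo from both allocation phases forms one group. SAP 5.13.2 counts events from randomization with no stated end and says: "These summaries will include number and percentages of subjects with TEAEs. Treatment comparisons will be carried out using Fisher's exact Test." SAP 5.13.3 treats deaths, serious events and discontinuations due to adverse events in the same way, and adds that "the proportion of subjects within specific clusters of TEAEs will be summarized and treatment comparisons will be conducted using Fisher's exact Test". Abnormal "laboratory values at (1) anytime and (2) each post-baseline visit will be assessed using Fisher's exact test" (SAP 5.13.4). Vital signs, weight, ECG and eye findings also have both any-time and by-visit tables (SAP 5.13.5, 5.13.6, 5.13.8.3). Days of exposure are summarized by arm (SAP 5.13.1) but enter no comparison.

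**The concern.** A crude percentage is a fair comparison only if both groups were watched for about the same time. All 3 mg patients were randomized early, while most planned placebo patients were randomized later. A common early stop therefore shortens placebo follow-up more than 3 mg follow-up, and any event that accumulates with time will look more frequent on 3 mg.

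This falls on the arm's main purpose. Protocol 3.2 makes safety and tolerability the primary focus for 3 mg, and Protocol 5.5 justifies its 45 patients as safety information for further development. SAP version 2 adjusted the imaging analyses for the early stop but made no matching change to the adverse-event analyses.

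**Working it through.** The documents give no figure for this comparison, so I first check the sample sizes it uses: 380 × 0.85 = 323 (plan: about 320 completers) and 167 + 167 + 45 = 379 (plan: about 380). These agree.

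1. *Placebo randomized after 3 mg closes.* 167 − 45 = 122, and 122/167 = 73% of planned placebo. The share is smaller if enrolment stopped before 380.

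2. *Accrual (inferred).* Protocol 10.3.7 sets the safety interim when "data from approximately 130 qualified patients at 12 weeks and 40 patients through 24 weeks have been obtained". With steady accrual and no losses between weeks 12 and 24, (130 − 40)/12 = 7.5 patients per week. Then 3 mg closes at week 135/7.5 = 18, and 380 would be reached at week 380/7.5 = 50.7. The Synopsis and SAP 5.16.1 still carry 105 and 75. I use 130 and 40 because the amendment summary says the lock would proceed on those counts.

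3. *Stop date (assumed).* One common stop, with a fraction f of 380 able to reach Week 52: stop week = 52 + f × 50.7. For f = 25% this is 64.7; for f = 40% it is 72.3. A majority without Week 52 means f below 50%.

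4. *Mean follow-up.* Follow-up is min(52, stop − entry), with placebo weighted 45 early to 122.5 late. Without dropout it is 51.2 weeks on 3 mg v 35.9 on placebo (f = 25%), or 52.0 v 41.7 (f = 40%). With 15% annual dropout it is 47.3 v 33.8, or 48.0 v 38.9.

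5. *Expected crude incidence, no drug effect.* With constant hazard, risk by week t = 1 − (1 − p)^(t/52), where p is the assumed one-year risk. Without dropout, 3 mg v placebo:
   - p = 60%: 59.4% v 45.7% (f = 25%), 60.0% v 51.2% (f = 40%)
   - p = 20%: 19.7% v 14.2%, 20.0% v 16.3%
   - p = 10%: 9.9% v 7.0%, 10.0% v 8.1%

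6. *Chance that Fisher's test (2-sided 0.05, about 45 v 167) flags 3 mg as worse when there is no effect.* Nominal upper tail 2.5%; ranges cover f = 25–40% and dropout 0–15%.

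| One-year risk | Constant hazard | Half the yearly hazard in the first 12 weeks |
|---|---|---|
| 60% | 13–36% | 7–15% |
| 20% | 7–15% | 5–9% |
| 5–10% | about 4–8% (just under 9% at 10% risk, f = 25%, no dropout) | about 4–5% |

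Against placebo randomized in the 1:1:1 phase the figure is no more than 2%.

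7. *Limits.* If only 10% reach Week 52, the 60% constant-hazard figure rises to 46–56%. Had the study run to completion, the bias would be nil. For events confined to the first 12 weeks it is also nil here, because the shortest follow-up is 64.7 − 50.7 = 14.0 weeks; under other accrual patterns tried, the null risk ratio for events in the first 4–12 weeks was 1.00–1.09. A smaller final N need not remove the bias: with 63 placebo patients (78-week accrual stopped at week 35), the null risk ratio at 20% risk was 1.30.

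8. *Remedy.* In the same scenarios, a log-rank test of time to first event using all placebo patients kept the upper-tail error at about 2–5%, with constant or front-loaded events.

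**The case against.** The strongest reply is that the documents show none of this directly. They give no stop date, accrual curve, number enrolled at termination or event rate. That stands, and every size above is a scenario. A reader might infer that the 3 mg comparisons are known to be biased, or that 73% of the actual placebo group is non-concurrent. The documents support only a probable direction, conditional on a common stop date, and a planned share.

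Second, the largest figures belong to common events accruing steadily, such as any TEAE. Deaths, serious events, adverse-event discontinuations and clusters are likely rarer, and at 5–10% risk the inflation is modest. That also stands.

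Third, the plan has safeguards. By-visit laboratory, vital-sign, ECG and eye comparisons match patients on time since randomization, which largely deals with unequal follow-up, although placebo still includes later entrants. Exposure days would show an imbalance, and SAP 5.7 has a log-rank test for all-cause discontinuation. But the TEAE-by-visit summary has no specified test or at-risk denominator, and the SAP 5.13.3 comparisons have no by-visit counterpart. Protocol 10.3.4 and SAP 5.1 permit additional analyses, but permission does not correct the rule as written.

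Fourth, relying only on placebo from the 1:1:1 phase would weaken detection of real harm. That is right, and it decides which analysis should lead.

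Two further readings are tempting and unsupported. 12 mg versus placebo is not affected, because those arms were 1:1 in both phases. Nor does the last-observation ANCOVA (SAP 5.1, 5.11.1) create a false efficacy claim for 3 mg: longer follow-up gives tau more time to rise, so the 1-sided test for benefit becomes conservative, and SAP 5.12.5 already plans annualized change for AV-1451, AV-45 and vMRI.

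**Conclusion.** The concern holds for 3 mg versus placebo, in the crude adverse-event comparisons and the any-time abnormality tables. The allocation switch, the early termination and the absence of follow-up from the comparisons are documented. The longer follow-up on 3 mg is an inference from them. The effect ranges from large for frequent, steadily accruing events to small for rare ones, and is near nil for events confined to the first weeks. It is worth fixing because it touches the purpose for which the arm was kept and the data are already in hand. The efficacy side is minor.

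**What to change.** For 3 mg versus placebo, add to SAP 5.13.2 and 5.13.3 a time-to-first-event analysis (Kaplan-Meier incidence and log-rank, as in SAP 5.7) for TEAEs, serious events, adverse-event discontinuations and each cluster, using all placebo patients.

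Preferably also stratify by randomization phase, to guard against drift in event rates over calendar time. A two-arm log-rank test stratified this way reduces exactly to the same-phase comparison, since nobody entered 3 mg after the switch. A phase-stratified Cox model with all three arms lets later placebo patients contribute indirectly through 12 mg, if the 12 mg effect is the same in both phases.

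As supportive analyses, show 3 mg against placebo randomized in the 1:1:1 phase, and exposure-adjusted rates with a note that they assume a roughly constant hazard. Interpret 3 mg safety from these alongside the crude tables, and 3 mg tau from the annualized change already planned.

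The cost is SAP wording, a censoring rule, an onset-date rule for incompletely dated events, and reruns; no new data are needed. The same-phase comparison is less precise: near 50% incidence its standard error is 0.5 × √(2/45) = 10.5 percentage points, against 0.5 × √(1/45 + 1/167.5) = 8.4. With full follow-up, exact Fisher power for 30% v 10% falls from 86% to about 57%. It should therefore supplement the other analyses, not replace them.
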